5.2.2. Treatment in children

Adamantane antivirals, although approved for use in children ≥ 1 year old (amantadine) and ≥ 13 year old (rimantadine) are not recommended for either treatment or prophylaxis due to widespread resistance and lack of activity against influenza B. Zanamivir is approved for treatment of influenza in children ≥ 7 years old but is not recommended in those with an underlying respiratory disease such as asthma because of the inhaled route of administration. Oseltamivir is approved for use in infants as young as 2 weeks of age for the treatment of influenza.

Prior to the 2009-2010 pandemic, fewer than 1% of children with influenza were treated with antiviral agents. Even among children hospitalized for influenza, only 2% to 37% (Garg, Fry et al. 2012, Poehling, Edwards et al. 2013) received an antiviral agent. During the pandemic, treatment rates increased markedly and 74% of hospitalized children were treated (Garg, Fry et al. 2012). At the time of the pandemic, OSE was approved for children aged \geq 1 year and ZNR was approved for children aged \geq 7 years. Subsequently, in 2012, OSE received approval for use in infants as young as 2 weeks old (Tamiflu® package insert, 2012). It is not clear if these increased rates of treatment have been maintained since the pandemic.

Recommendations regarding the use of antiviral agents were broadened after the H1N1 pandemic. The Advisory Committee on Immunization Practices (ACIP) produced guidelines in 2011 for the use of antiviral agents in influenza. ACIP recommended that antiviral therapy (NAIs but not adamantanes) be initiated as soon as possible for any patients with confirmed or suspected influenza with high severity, hospitalization or risk of complications. Use of antiviral therapy in the outpatient setting when risk factors were not present was left to clinical judgment as long as therapy could be initiated within 48 hours (Fiore, Fry et al. 2011).

The most recent American Academy of Pediatrics (AAP) (Pediatrics 2008) guidelines for the 2013-2014 influenza season are similar to and complement the ACIP's recommendations. The AAP reiterates that oseltamivir remains the drug of choice, simply because zanamivir is difficult to administer in children. Any child hospitalized or at increased risk of complications (see

Section 5.3.1) should receive antiviral therapy, even if influenza is only suspected but not proven and even if the patients present later than 48 hours after onset of symptoms. While the AAP acknowledges that most patients with uncomplicated influenza do not require treatment due to the self-limited nature of the infection, treatment should be offered to any child who would benefit from a decrease in duration of the clinical symptoms (Brady, Byington et al. 2013).

Just as with adults, the use of antiviral therapy (primarily OSE) in children has been demonstrated to shorten disease duration, improve complications, and reduce hospital stays. The length of illness is significantly reduced by 1.25 to 1.5 days in health children with confirmed influenza. Complications, particularly otitis media in children less than 5 year of age, are reduced with NAI therapy by 44-85%. Not surprisingly, the use of antibiotics is also reduced when NAIs are initiated promptly (Garg, Fry et al. 2012). In children hospitalized with influenza, if OSE was started within 24 hours of admission, length of stay was reduced by 18%. Intensive care unit (ICU) stay, mortality during hospitalization and readmission within 1 week of discharge were not statistically significantly different in OSE-treated and untreated subjects, which indicates that further study is needed regarding optimal inpatient treatment of children with influenza (Coffin, Leckerman et al. 2011).

5.2.3. Current need

Although OSE, an oral neuraminidase inhibitor pro-drug administered twice daily for 5 days, is widely used for the treatment of influenza, a need still exists for an effective treatment for adult and pediatric influenza patients who present in the urgent care, emergency department and in the hospital who may not be able to tolerate an oral or inhaled product, or where compliance with a 5-day treatment regimen is a concern. Such patients may include those who cannot comply with oral medications, those with poor history of compliance with oral medicines, those with gastrointestinal symptoms such as vomiting and diarrhea associated with influenza that could impair absorption of orally administered drugs, and those with gastrointestinal diseases that could impair drug absorption.

5.3.1. Clinical experience in adults

The pivotal study for the use of IV peramivir to treat subjects with acute uncomplicated influenza is Study 0722T0621, a Phase 2 double-blind, placebo-controlled, single dose study that enrolled 300 Japanese adult subjects with confirmed influenza. Both dosages of peramivir evaluated (single IV doses of 300 or 600 mg) significantly shortened the time to alleviation of influenza symptoms (duration of influenza, the primary endpoint) compared with placebo.

Studies BCX1812-211, BCX1812-311, and BCX1812-212 provide supportive data for the use of single parenteral doses of peramivir to treat influenza in the outpatient setting; in these studies, peramivir was administered as a single dose via bilateral intramuscular (IM) injections to subjects with influenza. Exposure to peramivir by IM administration is bioequivalent to exposure from IV administration (BCX1812-111 and BCX1812-113).

Study BCX1812-211 was a Phase 2, randomized study that enrolled 344 subjects with acute, uncomplicated influenza who received placebo, 150 mg peramivir or 300 mg peramivir as a single, divided IM dose. Study BCX1812-311 was similar in design and was planned as a Phase 3 study, but was terminated early after 82 subjects had enrolled and were randomized 2:1 to receive placebo or 300 mg peramivir in a single, divided IM dose. The study was terminated in order to study higher doses using a product with a higher concentration in subsequent studies. These 2 studies had almost identical eligibility criteria, had identical primary and secondary efficacy endpoints, and were conducted in successive influenza seasons. When the results from studies BCX1812-211 and BCX1812-311 were retrospectively combined in a post-hoc analysis, both primary and secondary endpoints for peramivir-treated subjects were improved compared to placebo.

Study BCX1812-212 was a placebo-controlled study of 405 subjects who were randomized 1:1 to receive either placebo or 600 mg of peramivir as a single divided IM dose. This study was conducted during a season in which the dominant circulating strain of influenza A showed reduced susceptibility to peramivir, and the results showed a non-significant trend favoring peramivir in the primary endpoint of time to alleviation of symptoms.

Two additional outpatient studies in adults occurred. Study 0815T0631 was a double-blind, double-dummy study of 1099 subjects from Japan, Taiwan and South Korea who were randomized to receive a single dose of IV peramivir (300 mg or 600 mg) or 5 days of oral OSE BID. For the primary endpoint of time to alleviation of symptoms, both peramivir treatment regimens were non-inferior to OSE. Study 0816T0632 was a double-blind, non-controlled study in high-risk patients with influenza; in this study, the duration of influenza illness was shorter among subjects who received 600 mg doses of peramivir compared with those in the 300 mg treatment group, although the 90% confidence intervals (CI) overlapped.

Hospitalized influenza was studied in BCX1812-201, a randomized, double-blind, trial of treatment with OSE 75 mg twice daily for 5 days, or IV peramivir 200 mg once daily, or 400 mg once daily. The study enrolled 122 evaluable subjects and employed an exploratory primary endpoint of "time to clinical stability." Compared to oral OSE given for 5 days, IV doses of peramivir 200 mg and 400 mg had similar effects on the novel exploratory endpoint. Among the secondary endpoints, the median time to resumption of ability to perform usual activities was approximately 4 days shorter for subjects treated with either dose of peramivir compared with OSE. Viral titers decreased rapidly among patients with influenza A after treatment with either OSE 75 mg twice daily or peramivir 200 mg or 400 mg daily. Among subjects with influenza B, numerical trends suggest more rapid reduction in viral titer with peramivir than OSE and greater activity of peramivir 400 mg than peramivir 200 mg.

During the 2009-2010 pandemic, BCX1812-303, an open-label Phase 3 study of peramivir 300 mg BID or 600 mg once daily (QD) enrolled 230 evaluable adult and 4 evaluable adolescent hospitalized subjects with confirmed or suspected influenza infection. The primary endpoint was the reduction in influenza virus titer measured by $log_{10}50\%$ tissue culture infective dose (TCID₅₀). There were no differences in either the mean or median values in the 300 mg BID or 600 mg QD treatment groups. By 48 hours after the beginning of peramivir treatment, 86% of all subjects with positive baseline titers in the intent to treat infected (ITTI)population had a negative virus titer (80% in the 300 mg BID group and 91% in the 600 mg QD group, as measured by log_{10} TCID₅₀.

BCX1812-301, a Phase 3, multicenter, randomized, double-blind, controlled-study of peramivir evaluated the efficacy and safety of peramivir administered IV in addition to standard of care compared to standard of care alone in subjects who were hospitalized due to influenza. The study failed to demonstrate a significant difference between treatment with placebo and standard of care and treatment with peramivir (600 mg IV, daily for 5 or 10 days) and standard of care for the primary endpoint of time to clinical resolution. A futility analysis was performed, and the study was terminated early at which point 338 evaluable (i.e. ITTI) subjects were enrolled (116 randomized to placebo and 222 randomized to peramivir).

Safety of various doses of peramivir in acute uncomplicated influenza has been evaluated in 1453 adults. The most frequently observed treatment emergent AEs (TEAEs) across all adult subjects with acute uncomplicated influenza treated with various doses of peramivir were diarrhea (7.4%), decreased neutrophil count (5.5%), and increased blood glucose (5.0%). The only events reported in $\geq 2\%$ of subjects treated with peramivir 600 mg and for which the rate was greater than placebo were diarrhea (7.6% vs. placebo 7.0%), decreased neutrophil count (5.7% vs. placebo 0.0%), hyperglycemia (5.3% vs. placebo 4.8%) and urine leukocytes (2.8% vs. placebo 1.8%). Adverse event rates overall were similar to placebo and OSE. No safety signals have emerged from these trials.

The safety of various doses of peramivir in hospitalized influenza has been evaluated in 355 adults in studies with active or placebo control (BCX1812-201 and 301) and 230 adults in an open label study with 2 different peramivir dosing regimens (BCX1812-303). The hospitalized population was comprised of acutely ill subject; many critically ill infected with both pandemic and seasonal influenza strains. Overall, peramivir had a favorable safety profile. In controlled trials, the most common adverse events in patients receiving various doses of peramivir with and without other NAIs were diarrhea (6.8%), nausea (4.8%), and insomnia (3.9%). The only events reported in \geq 2% of subjects treated with peramivir 600 mg monotherapy (no additional NAI) and for which the rate was greater than placebo were constipation (4.0% vs. placebo 2.0%), elevated creatine phosphokinase (CPK) (4.0% vs. placebo 0%), insomnia (3.0% vs. 0%), aspartate aminotransferase (AST) increase (3.0% vs. placebo 2.0%), hypertension (2.0 vs. placebo 0%) and hypokalemia (1.0% vs. placebo 0%).

In the open label trial, subjects in both arms receive a total daily dose of 600 mg peramivir (or equivalent in those subjects with renal function adjusted dosing). This trial ran from October 2009 to October 2010 and enrolled primarily subjects infected with pandemic H1N1 virus (74% of the ITTI population). A total of 10% of all subjects in the Safety population died. Nearly half of all deaths were related to respiratory failure reflecting the severity of the pandemic. Most adverse events were attributable to the underlying infection and comorbidities and no clinically relevant differences in safety outcomes were noted between the two dosing regimens. The most common adverse events were constipation (13.0%), diarrhea (12.6%), hypokalemia (9.6%), anemia (7.8%), hypotension (7.8%), nausea (7.8%), peripheral edema (7.8%), insomnia (7.4%) hyperglycemia (6.1%) hypertension (6.1%) and headache (5.2%).

5.3.2. Clinical experience in children

There have been 3 clinical trials that enrolled children. Study 0918T0633 was an open label study in acute uncomplicated influenza. In addition, there were 2 studies in hospitalized influenza that enrolled children, BCX1812-303 and BCX1812-301.

5.3.2.1. Study 0918T0633

Study 0918T0633 was a Japanese non-controlled, open-label study conducted in pediatric subjects with influenza (either inpatient or outpatient) that ran from September 2009 to December 2009. A total of 117 subjects, aged ≥ 28 days to < 16 years, were enrolled of which the ITTI analysis set was 112. The study excluded children with significant comorbidities such as encephalopathy, epilepsy, chronic respiratory disorders, congestive heart failure, immunosuppression and renal failure. Subjects were treated with peramivir 10 mg/kg (maximum dose 600 mg) IV for up to 5 days. This dose was believed to provide children with an adult equivalent of 300 to 600 mg peramivir a day. Two subjects received 2 doses, and the rest received a single infusion. The primary endpoint was the median time to alleviation of influenza defined as mild to no cough or nasal discharge and normal body temperature. Overall the median time was 27.9 hours (95% CI 21.7-31.7) with no differences noted between the age groups of 28 days to < 2 years, 2 to < 6 years, 6 to < 12 years, and 12 to < 16 years of age. Normal temperature of < 37.5°C was recovered in a median time of 20.4 hours (95% CI 19.1-20.9). If all influenza symptoms, including cough, sore throat, headache, nasal discharge, fever, myalgia/arthralgia and fatigue were taken into consideration, the median time to alleviation of symptoms was 30.5 hours (95% CI 22.6-45.8) with sore throat taking the longest to resolve. The median time to resuming activities of daily living (ADLs) was 103.0 hours (95% CI 94.9 hours- 119.6 hours) and ranged from 54.7 hours to 126.8 hours in the consecutive age brackets.

Adverse events were experienced by 62.4% of subjects. In the various age brackets (28 days to < 2 years, 2 to < 6 years, 6 to < 12 years, and 12 to < 16 years of age) the incidence for AEs ranged from 54.1 to 75% and tended to be higher for patients under 12 years. No deaths occurred but 2 subjects experienced serious adverse events (SAEs): influenzal pneumonia in one and pneumonia and encephalopathy in the other. Both children recovered. Most AEs were mild to moderate (79.5%). Overall, the most frequent TEAEs were decreased neutrophil count (21.4%), diarrhea (16.2%), vomiting (9.4%), and increased eosinophil count (7.7%). Of note, there were 3 subjects (2.6%) who experienced abnormal behavior.

5.3.3. Post marketing experience in children

Peramivir hydrate for injection was first approved in Japan on 13 January 2010 under the trade name Rapiacta® by Shionogi & Co., Ltd. for the treatment of viral infection with influenza type A and type B. Marketing authorization for the treatment of children and infants ≥ 28 days of age was obtained in Japan in October, 2010. Since that time 3 post marketing surveillance studies

have been performed, including one exclusively enrolling pediatric patients. The other 2 studies (one in routine use and one in high risk patients) allowed enrollment of subjects \geq 15 years old and any age child respectively.

The pediatric post-approval observational safety and effectiveness surveillance study was carried out between October 2010 and February 2012 in a routine pediatric setting and evaluated patients < 15 years of age. A total of 1,254 patients were evaluated at 173 institutions in Japan. The safety evaluable population was 1,199 and the efficacy evaluable population was 1186. Most patients (79.4%) had type A influenza and 13.2% of the patients were considered high risk.

There were 654 (54.5%) male and 545 (45.5%) female patients in the safety evaluable group. Fifty-four patients (4.5%) were < 1 year of age, including 1 patient who was < 4 weeks of age. Forty-four percent of the patients (527) were \geq 1 to < 7 years of age, and 51.4% (616 patients) were \geq 7 to < 15 years of age. A special safety analysis compared patients < 2 years of age and those \geq 2 years of age, and found that there were no significant differences in the incidence of AEs or the types of AEs in infants and toddlers versus older children.

Almost all patients (1008, 84.1%) received peramivir within 1 day of the start of influenza symptoms. Most patients were treated in an outpatient setting, but 138 (11.5%) were hospitalized for influenza, and 11 patients had serious influenza, defined as either influenza encephalopathy or the need for mechanical ventilation. Almost all patients (96.7%) received only 1 day of treatment with peramivir.

5.4. Rationale for Study

There remains a significant unmet need for influenza therapies in children. Currently, the only available options are oral or inhalation, both of which have limitations, both in terms of administration and viral resistance. Peramivir has demonstrated efficacy and safety when used in acute uncomplicated influenza in adults. However, there is significant clinical and real world experience with pediatric use indicating that there is both efficacy and safety when used in healthy and high-risk children as young as 28 days. Most children treated to date have been Asian, so the current study will provide valuable information in other racial and ethnic groups.

Because children bear a larger burden of infection during seasonal influenza and are at greater risk for complications during pandemics, new treatments for children are needed. During the last pandemic of 2009-2010, the rates of hospitalization, admission to intensive care units, and invasive life support were higher than for past seasonal influenza with the highest proportion of seriously ill patients being children and young adults (Dominguez-Cherit, Lapinsky et al. 2009,

Jain, Kamimoto et al. 2009, WHO 2009). The approved dose of peramivir in adults is a single dose of 600 mg because of improved efficacy without an increase in safety risk. Population pharmacokinetic modeling performed by the FDA (July 2009) based on the Shionogi Studies 0816T0633 (children and adolescents) and 0722T0621 (adults) supports a target dose of 12 mg/kg/day in children (6 to 12 years) to attain exposures similar to that in adults who receive a 600 mg IV dose.

In order to provide recommendations for dosing in subjects less than 6 months of age, an updated population PK model was developed that included all available data from adult and pediatric studies, and data from an interim review of BCX1812-305. Simulations from this model indicate that a dose of 8 mg/kg/day in children from birth to < 6 months of age should provide exposure of peramivir similar to that observed in adult subjects and pediatric subjects who have completed BCX1812-305. In subjects 6 month of age and older, a 12 mg/kg dose is simulated to attain exposures in pediatric subjects similar to that in adults administered a 600 mg IV dose. Simulations indicate that in subjects < 6 months of age, the predicted exposure following an 8 mg/kg dose will not exceed that of adults.

There is ample clinical and real world experience with peramivir. A large number of children have been treated in post-marketing without new safety signals arising, other than those already identified with other NAIs. Events of abnormal behavior have been reported occurring primarily in children and the elderly, often in those with underlying neurologic conditions. In addition, very rare hypersensitivity reactions including, anaphylaxis, erythema multiforme and Stevens-Johnson Syndrome have occurred in the post-marketing setting, although as with all NAIs, it is difficult to know if this is due to concomitant medications, the viral infection, or the NAI. Many studies have reported benefits of NAIs in shortening complications, hospital stays and antibiotic use. Overall it is expected that the benefit risk ratio of peramivir will be favorable in children.

6. TRIAL OBJECTIVES AND PURPOSE

6.1. Primary objective

• To evaluate the safety of IV peramivir compared to oral oseltamivir in pediatric subjects with acute uncomplicated influenza (here within referred to as influenza)

6.2. Secondary Objectives

- To describe the pharmacokinetics of IV peramivir in pediatric subjects with influenza
- To evaluate the effectiveness of IV peramivir compared to oral oseltamivir in pediatric subjects with influenza
- To evaluate the incidence of influenza complications, specifically otitis media, sinusitis, bronchitis or pneumonia requiring antibiotic use diagnosed after initiation of study drug

7. INVESTIGATIONAL PLAN

7.1. Endpoints

7.1.1. Primary Endpoint

The primary endpoints of this study will be assessment of adverse events, laboratory analyses (clinical chemistry, hematology and urinalysis), vital signs and physical examinations.

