- Subjects 28 days to < 13 years of age will receive a weight-based dose administered as a capsule or oral suspension (twice daily for 5 days).

Note, as of the approval of amendment 3, no additional subjects will be randomized to receive oseltamivir.

Criteria for evaluation:

Safety:

• Safety will be evaluated through assessments of Adverse Events (AEs), laboratory analyses (clinical chemistry, hematology and urinalysis), vital signs, and physical examinations. A review and summary of safety utilizing all collected assessments will be performed by a Data Safety Monitoring Committee (DSMC) after each influenza season as outlined in the DSMC charter.

Pharmacokinetic:

• Plasma peramivir concentrations will be measured by a validated liquid chromatography-tandem mass spectrometry (LC/MS-MS) assay. Concentrations will be utilized in determination of population pharmacokinetic parameters.

Effectiveness:

- **Clinical:** Time to resolution of fever; time to resolution of influenza symptoms (per the age appropriate symptoms);
- **Virologic:** Viral shedding; virus susceptibility.

Statistical methods:

Sample Size:

The study is designed to evaluate the safety and pharmacokinetics of IV administration of peramivir in pediatric subjects with influenza. The sample size is adequate to evaluate these objectives. Descriptive comparison between peramivir and oseltamivir treated subjects will be performed where possible. Formal hypothesis testing will not be performed.

Safety:

Qualitative analyses will be performed for AE type, frequency and severity, as well as vital sign absolute values, clinical laboratory absolute values, and physical examination findings and their respective changes from Baseline for all subjects.

Pharmacokinetics:

Plasma concentrations and covariates of interest will be evaluated in a meta-population analysis using mixed effect modeling techniques to estimate population pharmacokinetic parameters in each age group and to identify pharmacokinetically-relevant covariates. Data from the completed pediatric study 0918T0633 of IV peramivir in Japan will be included in this analysis.

Effectiveness:

Clinical and virologic endpoints will be summarized using descriptive statistics.

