11.4. Physical Examination and Influenza-Related Complications Assessment

The Investigator will perform a full physical examination at Baseline, including the subject's height or length and weight. At each follow-up visit, study personnel will evaluate the subject for the presence of clinical signs and/or symptoms of the following influenza-related complications: sinusitis, otitis media, bronchitis and pneumonia.

If the Investigator determines that the subject has (or is presumed to have) one of the influenza-related complications noted above, he/she will note that in the subject's source documents and on the influenza-related complications CRF page. Any medication used to treat the condition must also be recorded (on the concomitant medication page). The Investigator will promptly provide appropriate treatment for any suspected or proven influenza-related complication(s). Signs and symptoms associated with influenza-related complications will not be reported on the adverse event CRF page unless they meet criteria for an SAE.

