13.9. Safety Analyses

Adverse Events will be mapped to a Medical Dictionary for Regulatory Activities (MedDRA)-preferred term and system organ classification. The occurrence of treatment-emergent AEs (TEAEs) will be summarized by age group and treatment group using MedDRA-preferred terms, system organ classifications, and severity. All AEs will be listed for individual subjects showing both verbatim and preferred terms. Separate summaries of treatment-emergent SAEs and AEs related to study drug will be generated.

Descriptive summaries of vital signs and clinical laboratory results will be presented by age group, treatment group and study visit. Laboratory abnormalities will be graded according to the DAIDS Table for Grading Adverse Events for Adults and Pediatrics (Publish Date: December 2004 Clarification, 2009, see Appendix 1). The number and percentage of subjects experiencing treatment-emergent graded toxicities will be summarized by age group and treatment group. Laboratory toxicity shifts from baseline to post-baseline assessments will be summarized by age group and treatment group.

Previous and concomitant medications will be mapped to a WHO preferred term and drug classification. The number and percent of subjects taking concomitant medications will be summarized using preferred terms and drug classifications.

The number and percent of subjects experiencing influenza related complications will be summarized by age group and treatment group.

Subject disposition will be presented for all subjects. The number of subjects who completed the study and discontinued from the study will be provided. The reasons for early discontinuation also will be presented.

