#### **6.3.3.** Clinical Laboratory Assessments

Descriptive summaries of the following selected (quantitative) clinical laboratory results will be presented by study visit and treatment group for each age group and overall: ALT, AST, Serum Creatinine, BUN, HGB, Albumin, and Alkaline Phosphatase. Laboratory abnormalities (toxicities) will be graded according to the DAIDS Table for Grading Adverse Events for Adults and Pediatrics (Publish Date: December 2004). The number and percentage of subjects experiencing treatment-emergent graded toxicities will be summarized by treatment group for each age group and overall. Laboratory toxicity shifts from baseline to Day 7 will be summarized by treatment group for each age group and overall.

All laboratory toxicities that occurred before the initiation of study treatment or more than 14 days post study drug discontinuation will be excluded from the tables but will be included in the listings.

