# **6.3.4.** Other Safety Analyses

Descriptive summaries of vital signs will be presented by study visit and treatment group for each age group and overall.

All abnormal physical examination findings will be summarized by study visit and treatment group for each age group and overall.

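### Physical-examination change from Baseline cannot be produced from a Baseline-only schedule, and the SAP's quantitative laboratory summaries leave out neutrophils without declaring it

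*Protocol*

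**What the plan says.** Protocol 7.1.1 reads: "The primary endpoints of this study will be assessment of adverse events, laboratory analyses (clinical chemistry, hematology and urinalysis), vital signs and physical examinations".

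**Physical examination.** The safety paragraph of the synopsis's statistical methods commits to "physical examination findings and their respective changes from Baseline for all subjects". Protocol 11.4 sets the timing: "The Investigator will perform a full physical examination at Baseline, including the subject's height or length and weight". Table 1 of the protocol and the schedule in SAP 2.2 agree with 11.4. Footnote 6 of Table 1 allows a targeted examination later, but only when an influenza-related complication is suspected. SAP 6.3.4 then plans this output: "All abnormal physical examination findings will be summarized by study visit and treatment group".

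**Laboratory.** Protocol 13.9 states: "Descriptive summaries of vital signs and clinical laboratory results will be presented by age group, treatment group and study visit". The same synopsis sentence covers laboratory values and their changes from Baseline. SAP 6.3.3 restricts the quantitative summaries to "ALT, AST, Serum Creatinine, BUN, HGB, Albumin, and Alkaline Phosphatase". It keeps graded toxicities and toxicity shifts to Day 7 without any restriction by analyte. SAP section 7 lists one change from the protocol, an analysis of antipyretic doses, and anticipates no others.

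**The concern.** Safety is the primary objective and Protocol 13.3 rules out formal hypothesis tests, so the descriptive safety tables are the primary result. A table planned by study visit suggests follow-up data. For the full examination the only scheduled visit is before dosing, and it cannot inform the comparison of peramivir with oseltamivir.

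The laboratory list leaves out results that the protocol's own background reports. Decreased neutrophil count was the most frequent treatment-emergent event in Study 0918T0633 (21.4%, Protocol 5.3.2.1). In adults on 600 mg with uncomplicated influenza it was 5.7% against 0.0% on placebo (Protocol 5.3.1). Hemoglobin is the only hematology value summarized quantitatively. A general downward shift in neutrophils that seldom reached a grade could pass without any table showing it.

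**Working it through.** The plan gives no sample-size or power figure to reproduce for this point. The check compares sections and counts.

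**1. Examination schedule.** Protocol Table 1 marks Physical Exam once, in the Baseline pre-dose column. The post-dose columns are Day 1 post-dose, Day 3, Day 7, Day 14 and Early Withdrawal: 0 of 5 are marked. Protocol 10.2.2.2 to 10.2.2.6 list no physical examination at these times, only a complications assessment from Day 3 onward. A change needs a post-dose value for each subject, and none is scheduled. Table 14.3.7 would therefore hold one scheduled pre-dose visit plus whatever targeted examinations occurred.

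**2. Laboratory coverage.** Protocol 11.2.1 lists 20 chemistry analytes. Protocol 11.2.2 collects a complete blood count with differential at Baseline and Day 7. SAP 6.3.3 names seven analytes: ALT, AST, creatinine, BUN, albumin and alkaline phosphatase (6 of the 20), plus hemoglobin. Neutrophils, eosinophils, glucose and creatine kinase are absent.

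**3. Size of the earlier neutrophil finding.** Study 0918T0633 enrolled 117 subjects: 0.214 × 117 = 25.04, so about 25 subjects (25/117 = 21.37%).

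**4. What still carries neutrophils.**
- Table 14.3.5.2, graded toxicities. Absolute neutrophil count has a row in protocol Appendix 1.
- Table 14.3.5.3.2, hematology shifts, which SAP 6.3.3 describes as toxicity shifts.
- The treatment-emergent AE tables, if a result is judged clinically significant (Protocol 11.2.2).
- Listing 16.2.8.1.1.

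**5. What is lost.** Above 7 days of age, Grade 1 covers 1,000 to 1,300/mm3, and Appendix 1 says values between the normal limit and Grade 1 are not graded. As an assumed illustration, not trial data, take a fall from 6,000 to 1,400/mm3: (6,000 − 1,400)/6,000 = 77%. It receives no grade and no shift. Unless reported as an AE, it appears only in the listing.

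**6. Other named analytes.** Increased eosinophil count was the fourth event listed in the pediatric study (7.7%). Appendix 1 has no eosinophil row, so graded and shift tables based on it cannot show eosinophils at all. Elevated creatine phosphokinase was 4.0% against 0% on placebo in hospitalized adults on 600 mg monotherapy. Hyperglycemia was 5.3% against 4.8% on placebo in adults with uncomplicated influenza. Both have DAIDS grades but no quantitative summary.

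**The case against.** A reader might infer that the laboratory component is not delivered, or that a neutrophil fall would appear in no summary. The documents do not support that. Graded toxicities and shifts remain by age and treatment group, and clinically significant results become AEs. The 21.4% and 5.7% figures are themselves AE rates, so they came through a route this trial keeps. This stands, and it limits the loss to the by-visit value and change.

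A reader might also take neutrophil decrease as an acknowledged safety signal. The protocol does not say so: the pediatric study was uncontrolled, and Protocol 5.3.1 states that the adult trials in uncomplicated influenza raised no safety signals. The case for adding the analyte rests on its frequency, not on established harm. The case for glucose is weaker because its rate was close to placebo. The protocol cites no result from previous trials for WBC or platelets.

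On the undeclared narrowing, Protocol 13.9 does not say every analyte, Protocol 13.2 leaves technical detail to the SAP, and the SAP (dated 11 July 2016) refers to protocol version 4.0 while the protocol in hand is Version 6.0. So it cannot be shown that the SAP departed from the protocol in force when it was written. It can be shown that the current pair do not agree.

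On examinations, the protocol points readers to the schedule of assessments, and the promise of change appears only in the synopsis. Protocol 13.9 plans no examination analysis, and abnormal findings by visit can be tabulated from Baseline and targeted examinations. This makes the problem one of wording, but the synopsis promise still cannot be met. Nor does it mean that children go unassessed after dosing: vital signs, complication assessments and AEs are collected at Days 3, 7 and 14, except that a Day 14 phone contact covers only complications, medications and AEs.

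**Conclusion.** The point holds in two limited parts. First, the full physical examination is named in the primary endpoint but has 0 of 5 post-dose columns marked, so change from Baseline for all subjects cannot be produced. Second, the laboratory component is partly delivered. Seven analytes receive quantitative summaries, neutrophils do not, and SAP section 7 is silent on the restriction. The loss is the by-visit neutrophil value and change, including falls that stay above 1,300/mm3 (beyond 7 days of age) and are not reported as AEs. For eosinophils the loss is larger, because no grade exists.

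This assumes that the shift tables use toxicity grades, as SAP 6.3.3 says, and that the graded tables include every DAIDS parameter collected. How many children would have an ungraded fall cannot be estimated from the documents.

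**What to change.** (a) In SAP 6.3.3 and Table 14.3.5.1, add neutrophils, eosinophils, glucose and creatine kinase. Show value and change from Baseline by age group and treatment group, in the Safety population. WBC and platelets are optional.

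(b) In the synopsis, Protocol 7.1.1 and SAP 6.3.4, state that the full physical examination is a Baseline assessment, and delete the promised change from Baseline for it. Keep any post-dose targeted-examination findings in Table 14.3.7, which uses the Safety population. Moving them to the complications table (14.2.4) would restrict them to the ITTI population and drop treated children without RT-PCR-confirmed influenza from a safety summary.

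The cost is wording changes and a few extra rows in one table. The analytes come from samples already scheduled at Baseline and Day 7, so no visit or blood draw is added. The downside is that the primary endpoint claims slightly less than it does now. The change adds no post-dose examination; it makes the stated endpoint match what is collected.
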